Statistical Analysis Plan

Study Title: RSV Antibiotic Drivers and Resource-use (RADAR)

Document Date: May 10, 2025

NCT Number: Pending

Version: 1.0

1. Objectives

- To identify clinical, laboratory, and radiologic factors associated with antibiotic use in RSV-positive pediatric patients.
- To evaluate the impact of antibiotic use on hospital stay duration and treatment cost.

2. Study Design

This is a retrospective, single-center, observational comparative study conducted at [name] Uz Children's Hospital between April 2017 and April 2021. Children aged 1 to 24 months with laboratory-confirmed RSV-positive acute lower respiratory tract infections were included.

3. Study Population and Variables

- Population: RSV-positive children aged 1 to 24 months.
- Primary Variables: CRP, WBC, chest radiograph findings, presence of fever.

- Antibiotic-related Variables: Class/type of antibiotic used, timing of initiation, duration.
- Outcome Variables: Length of hospital stay, total cost of hospitalization.

4. Statistical Methods

- Statistical analyses were performed using SPSS Statistics v24.0.
- Categorical variables were compared using Pearson's Chi-square test or Fisher's exact test when appropriate.
- Continuous variables were analyzed using the Mann-Whitney U test or t-test based on normality assumptions.
- Multivariate logistic regression was used to identify independent predictors of antibiotic continuation.
- A p-value less than 0.05 was considered statistically significant.

5. Handling of Missing Data

Patients with incomplete clinical, laboratory, or radiologic data were excluded from the study and not included in the final analysis.

6. Cost Analysis

A micro-costing method was used based on hospital billing records. Costs were calculated in Turkish Lira (TRY) and then converted to U.S. Dollars (USD) using the average exchange rate between 2020 and 2022: 1 USD = 7.7784 TRY.

7. Ethical Considerations

The study was approved by the Ethics Committee of [name] Uz Children's Hospital (Approval No: 2021-634). All data were anonymized and handled in compliance with institutional and international ethical standards.

8. Document Control

- Author: [name]
- Affiliation: Ege University Faculty of Medicine, Department of Pediatric Cardiology
- Version: 1.0
- Date: May 10, 2025

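### SAP section 5 applies complete-data exclusion to the whole study, so the stay and cost comparison can lose children whose missing values it never uses

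*SAP*

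**What the plan says.** Section 5 of the SAP consists of one rule: "Patients with incomplete clinical, laboratory, or radiologic data were excluded from the study and not included in the final analysis". It does not say which variables must be complete, and it sets no separate condition for each analysis.

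The population is defined elsewhere without a completeness condition. Section 2 states: "Children aged 1 to 24 months with laboratory-confirmed RSV-positive acute lower respiratory tract infections were included". Section 3 repeats the age and RSV criteria: "Population: RSV-positive children aged 1 to 24 months".

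The second objective in section 1 is "To evaluate the impact of antibiotic use on hospital stay duration and treatment cost". Section 3 gives the matching endpoints: "Outcome Variables: Length of hospital stay, total cost of hospitalization". For continuous variables, section 4 offers only this: "Continuous variables were analyzed using the Mann-Whitney U test or t-test based on normality assumptions". Section 6 takes costs from the hospital's billing records.

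The one multivariable analysis is in section 4: "Multivariate logistic regression was used to identify independent predictors of antibiotic continuation". Its covariates are not listed. The likely candidates are in section 3: "Primary Variables: CRP, WBC, chest radiograph findings, presence of fever".

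**The concern.** The rule is stated openly; the difficulty is its reach. A comparison of stay or cost between antibiotic groups by a t-test or Mann-Whitney test needs two facts per child: the group and the outcome. Under section 5, a child with both can still be removed because a blood test or radiograph is absent. The plan lists no adjusted model for stay or cost, so covariate adjustment does not explain the exclusion.

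The logistic model does need its predictors, so complete-case fitting is an understandable default there. But the data are retrospective and the SAP describes no fixed work-up. Whether a test was recorded could relate to the child's presentation and to the antibiotic decision. With no exclusion count and no comparison of the two sets of children, a reader cannot judge how far the analysed children represent the population in sections 2 and 3, or whether selection touched the odds ratios.

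**Working it through.** **What each analysis needs, against what section 5 demands**

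| Analysis | Data the listed method uses | Effect of section 5 |
|---|---|---|
| Length of stay by antibiotic group | group, stay | also requires complete clinical, laboratory and radiologic data |
| Cost by antibiotic group | group, billed cost | same |
| Logistic model of continuation | continuation, predictors | complete-case |

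The first two rows carry the point. They rest on two readings: that the laboratory and radiologic data meant in section 5 include CRP, WBC and radiograph from section 3, and that stay and cost fall under the continuous variables of section 4. Both are natural readings, but neither is spelled out.

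**Figures in the plan.** There are none to reproduce. The SAP gives no sample size, power, missing-data rate or number excluded, so everything below is illustration.

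**Precision of the stay and cost comparison**

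Assumptions: each variable is missing in a share *m* of children (5% or 10%); the loss is unrelated to antibiotic group or outcome; power is 80% in all children; the test is two-sided at 0.05 (section 4 gives 0.05 but not the sidedness).

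- Share kept, *r*: 1 − *m* if the same children lack every item; (1 − *m*)^k if *k* items are missing independently.
- Standard error ratio: 1/√*r*.
- Power: Φ((1.960 + 0.842)√*r* − 1.960).

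Worked case, *m* = 5%, three items, independent: *r* = 0.95³ = 0.857; 1/√0.857 = 1.080; 2.802 × 0.926 − 1.960 = 0.634; Φ(0.634) = 0.737.

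| *m* | Pattern | Kept | SE ratio | Power |
|---|---|---|---|---|
| 5% | fully overlapping | 95% | 1.026 | 78% |
| 5% | CRP, WBC, radiograph independent | 86% | 1.080 | 74% |
| 5% | those three plus fever, independent | 81% | 1.108 | 72% |
| 10% | fully overlapping | 90% | 1.054 | 76% |
| 10% | CRP, WBC, radiograph independent | 73% | 1.171 | 67% |
| 10% | those three plus fever, independent | 66% | 1.235 | 62% |

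The rows with fever apply only if the clinical data in section 5 are taken to include it.

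**Odds ratios in the logistic model**

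Suppose completeness depends only on continuation and one binary predictor, say fever. Write the probabilities of being complete as s11 (continued, fever), s10 (continued, no fever), s01 (not continued, fever) and s00 (neither). The complete-case fever odds ratio is then the full-data one multiplied by (s11 × s00)/(s10 × s01).

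- Depends on continuation only (90/90/60/60%, in the order s11/s10/s01/s00): 0.90 × 0.60/(0.90 × 0.60) = 1.00.
- Depends on fever only (90/60/90/60%): 0.90 × 0.60/(0.60 × 0.90) = 1.00.
- Joint, not factorising (95/90/85/60%): 0.95 × 0.60/(0.90 × 0.85) = 0.745, so an odds ratio of 2.00 becomes 1.49.
- Joint, not factorising (90/70/70/65%): 0.90 × 0.65/(0.70 × 0.70) = 1.194, so 2.00 becomes 2.39.

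The last two patterns were chosen to show that bias can run either way. Nothing in the documents points to them.

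**The case against.** The strongest reply is that section 5 works as an eligibility condition: the study concerns children with a full work-up, the plan says so, and one common sample keeps one denominator for both objectives. Part of this stands. A common sample is a legitimate convenience and the rule is not concealed. But sections 2 and 3 define the population without that condition. If it is intended, the conclusions need to be limited to children with complete data, and the exclusions still need counting.

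Second, the loss may be small. That is possible, and the documents cannot settle it; a count would.

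Third, the crude stay and cost contrast is confounded by severity, so restoring children mainly adds precision to a confounded comparison. That is correct. An adjusted comparison would itself need the missing covariates. No bias figure for stay or cost is claimed here.

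Fourth, the odds-ratio examples only return the completeness patterns put into them. That is also correct. A reader might infer from section 5 that the reported odds ratios are biased. The documents do not support this: dependence on the outcome alone, on a modelled predictor alone, or on both in a way that factorises leaves the odds ratio unchanged, and nothing shows which case applies.

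Finally, a reader might infer that no check is planned anywhere. That is established for the SAP only; the protocol was not available for this check and may hold an exclusion flow or a completeness criterion.

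**Conclusion.** The point holds as a defect of scope and reporting in the SAP. The text of section 5 applies completeness study-wide; that this costs the second objective children whose missing values its listed methods do not use follows from reading section 5 with sections 3 and 4. The SAP plans nothing that would let a reader see the effect.

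Its size is unknown. On the assumptions stated, and counting CRP, WBC and radiograph, the standard error rises by 3% to 8% at 5% missing per item and by 5% to 17% at 10%. Counting fever as well raises the upper ends to 11% and 23%. The power figures start from an assumed 80%, since the plan gives none. If loss differs between antibiotic groups or depends on outcome, these precision figures do not apply.

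For the logistic model, bias is possible but not shown. The point is worth fixing because the remedy is cheap, not because a large error has been demonstrated.

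**What to change.** Replace section 5 with a per-analysis rule:

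- All eligible RSV-positive children aged 1 to 24 months form the study population. Length of stay and cost are each analysed in every child with antibiotic group and that outcome recorded, whether or not CRP, WBC or radiograph is missing.
- The complete-case logistic model of continuation is kept. A multiple-imputation sensitivity analysis is added, with the model outcome and other recorded variables in the imputation model. Imputation suits a supporting role because a test may have gone unordered for reasons that were not recorded, which the missing-at-random assumption would not cover.
- The number with incomplete data is reported by variable and antibiotic group, and children with and without complete data are compared on variables recorded for both.

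Section 7 says the data were anonymized. If excluded records can no longer be linked, report the exclusion count by antibiotic group where available and limit the conclusions to children with complete data.

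The cost is SAP wording, modest extra analysis and some return to screened records. The change does not remove confounding by severity from the crude stay and cost comparison.
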